### **5.0 Study Procedures**

### 5.1 Baseline visit 1: Initial contact, screening, and consent

Interested respondents will be screened by a trained research staff over the phone or inperson, depending on the recruitment methods. For this research, no aspect of the participant's diabetes treatment regimen will be modified.

Those who are eligible for the study will be invited to the in-person visit. The first visit (i.e., Baseline visit 1) will be conducted at VUSN (Vanderbilt School of Nursing)'s lab at Wesley building.

At the Baseline visit 1, individuals will check their blood glucose level via finger prick. If their random glucose levels are between 80-300, they will complete the informed consent with assistance from the trained research staff. The trained research staff will complete baseline biometric assessment, including measure of height, weight, waist circumference, and blood pressure. Those who are consented will participate in: 1) completing survey questionnaires (30 minutes), 2) a baseline biometric assessment, 3) brief instruction regarding the wear of activPAL and continuous glucose monitoring (CGM) devices (30minutes), and 4) start to wear two devices for 7 days. The activPAL3 device (PAL Technologies Ltd., Scotland, UK) will be worn on the thigh and a CGM (Abbott FreeStyle Libre) will be attached to the upper arm. The research staff will provide: 1) a copy of the informed consent form; 2) instructions with photos and 5 waterproof dressings (Tegaderm) for attaching the activPAL on the thigh; 3) information about the CGM; and 4) daily sleep diary and wear log for 7 days. Participants will receive \$25 for baseline visit 1.

#### 1. Biometric assessments

Participants will undergo a basic physical examination (e.g., height, weight, blood pressure, hip circumference, waist circumference) and blood collection.

- A) Anthropometrics: Height, weight, and waist and hip circumferences will be measured using a validated stadiometer, digital scale, and flexible tape measure, respectively. All measurements will be recorded to the nearest 0.1 cm and 0.1 kg.
- B) Blood pressure: Blood pressure will be measured using an automated and validated BP monitor. In a private room, participants will be seated comfortably for 5 minutes with feet flat on the ground prior to measurements.32 The device will take three readings at 2-minute intervals and the mean of three BP readings will be recorded.

### 2. Questionnaires

Participants will be given an iPad to answer questions about their demographics, socioeconomic characteristics, and a series of questionnaires detailed below. All responses will be recorded in REDCap.

- A) **Demographics**: demographics and socio-economic status will be self-reported by the patients.
- B) Health behavior: Questions about their tobacco use, alcohol intake, physical activity will be measured using the 27-item International Physical Activity Questionnaire (IPAQ), and diet measured using the 16-item Rapid Eating and Activity Assessment for Participants Short Version (REAP-S). Sleep quality (measured using the 10- item Pittsburgh sleep quality index) will be answered with the assistance of the study team member.
- C) Confidence in reducing SB and increasing PA: Confidence in reducing SB and increasing physical activity will be measured using 12 items from the Self-Efficacy Questionnaire for Physical Activity and Sedentary Behavior (Cronbach's alpha = 0.79).
- D) Habit strength for SB: Habit strength for SB will be assessed by using a validated measure, Self-Report Habit Index (Cronbach's alpha = 0.91). This 7- item index was adapted to sedentary breaks (standing/walking) to assess the degree to which sedentary breaks become habitual.
- E) **Quality of life**: Quality of life will be measured using the Patient-Reported Outcomes Measurement Information System (PROMIS)-Global Health, a 10item measure developed by the NIH as an indicator for Healthy People.
- F) **Medical history and current medication**: Medical history and current medication will be self-reported by the patients through the Self-Administered Comorbidity Questionnaire (SCQ).
- G) **Diabetes self-management**: Self-efficacy of diabetes self-management will be measured by the Diabetes Self-Management Questionnaire (DSMQ).
- H) **Diabetes-related emotional distress:** The emotional impact of living with diabetes will be assessed using the Diabetes Distress Scale (DDS).
- I) Barriers to Physical Activity: Barriers to PA will be assessed using 11 items from the Barriers to Physical Activity in Diabetes (BAPAD1) questionnaire which asks about various factors such as the fear of hypoglycemia, concerns about losing control over diabetes, fear of fatigue, fear of injury, and other perceived barriers related to diabetes and physical health. Participants will

be asked to rate the likelihood of each item impeding their regular physical activity over the next 6 months on a scale ranging from 1 (extremely unlikely) to 7 (extremely likely).

#### 3. ActivPAL

The activPAL is a non-invasive method of monitoring activity and rest cycles through an inclinometer. The device will be worn on the anterior upper thigh of the dominant leg and kept in place by an adhesive pad (Tegaderm). If the participants have hair on the upper thigh, shaving an area of the thigh will be considered; we will provide a disposable shaving razor and foam as well as a private room with a sink. The participant will apply the device by themselves in a private room. The participants will wear the activPAL 24hours over a 7-day period. There is no need to charge the device. The activPAL monitor has been validated against direct observation and is the most sensitive device to detect sitting-to-standing transitions. At a follow-up visit (Baseline visit 2), the activPAL data will be downloaded to the secured PI's computer and summary reports will be reviewed by the study team member and the participants.

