#### 6. Fitbit

We will provide Fitbit (Inspire 3) to each participant. The Fitbit is not intended to be used as a medical device. All participants will have the ability to monitor physical activity, sleep, and heart rate with the Fitbit. All data from the Fitbit will be continuously streamed to the secure Fitbit servers. The study team member will assist participants in downloading the app and creating an account and will instruct them on how to use the device, with the official Fitbit user manual. When we create Fitbit accounts for research subjects, we do not use their real name or email address and default their account settings to the most privacy-protective option available.

Fitbit accounts require a unique email address for each user. To ensure participants' anonymity and privacy when creating Fitbit accounts, we will (1) set up anonymous Gmail accounts and (2) set up de-identified Fitbit accounts for the purpose of the study. This individualized email address will then be linked to a Fitbit account in which personal identifiers should not be used. Importantly, research staff and participants will be advised that the email and Fitbit accounts should be used strictly for the study's purpose.

Moreover, account information will be stored in protected PI's computer within encrypted documents. Once the intervention is concluded, Fitbit data will not be collected. Also, Fitbit and Fitbit app will be reset for the participant to keep using the Fitbit after study completion.

#### 5.2 Baseline visit 2

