### 5.2.2 Randomization

Once the data is downloaded and reviewed by the PI, the Study Team Member will use the REDCap randomization function and will inform participants of their group assignment (1:1 ratio).

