### 5.3.1 Instructional/goal setting session

The study team member will provide an orientation at the baseline visit 2. The study team member will review the activPAL data and identify targetable prolonged SB bouts. The study team member and the participant will set two goals:

1) a SB reduction goal will be set as reducing daily sedentary time gradually until they reach the goal of  $\ge$  120 minutes SB reduction; and 2) a sedentary break goal will be set as 3 minutes of standing/walking every 1 hour and then increasing its duration to 5 minutes and its frequency to every 30 minutes.

These goals were feasible in stroke patients and T2D patients. The participant will enter the goal into the Fitbit for self-monitoring and fill out the first worksheet in the Ten Top Tips (TTT). The TTT is a booklet developed from the Habit Formation Theory and includes 10 tips to add SB breaks into their daily routine. The ten tips are modified to eight in our study. See Appendix for the TTT and worksheet. This goal session will last approximately 1 hour.

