# 5.3.6 Control Group

The control group will receive the American Heart Association's Healthy Living booklet. Control group participants will receive all study assessment but will not be instructed to monitor sitting time. The Fitbit move alert setting will be disabled for the control group.

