### **5.4 Post-Intervention Visit**

After 8 weeks, all participants will be invited to an in-person visit (post-intervention visit). During the visit, all the above parameters will be re-measured by the same trained research staff. The visit will take about 1 hour including the completion of a series of questionnaires (which participants may complete beforehand) and biometric assessments. All participants will wear the activPAL3 and the CGM for 7 days to examine their post-intervention activity and glycemic control. They will return the devices via prepaid mail. All participants will receive \$50 for the post intervention visit, and an additional \$50 for mailing back the devices to the study team.

Therefore, total compensation would be \$150 for each participant. Also, all participants will be informed of their 24-hour glucose results and activity patterns retrieved from the activPAL device.

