### 8.0 Statistical Considerations

Based on Sit Less V1's (IRB #221566) effect size of 0.71 for reducing sitting time, we estimated a minimum sample size of 66. To assess the scalability of Sit Less V2, we aim to recruit 80 patients. Eligible participants will include T2D patients from VUMC who report sitting for over 10 hours daily, own a smartphone, and do not currently use an activity tracker. We will screen potential participants using VUMC's electronic health records (EHR) and send recruitment messages via the My Health at Vanderbilt app. According to our EHR search, we have 2,125 eligible patients, and with a 4% recruitment rate — as seen with enrolling 7 participants monthly from Sit Less V1 — reaching a target of 80 participants within 12 months is achievable.

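### As worded, section 5.1 has the baseline activPAL report reviewed with participants of both arms, so controls may receive one element of the intervention before the 8-week period

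*Combined protocol and SAP*

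**What the plan says.** Five places in the protocol bear on who sees the baseline activPAL report, and when.

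- Section 5.1, item 3 (ActivPAL) describes the device for everyone enrolled. Looking ahead to Baseline visit 2, it says that "summary reports will be reviewed by the study team member and the participants". No arm is named.
- Section 5.2.2 (Randomization) places allocation at a point defined as "Once the data is downloaded and reviewed by the PI". It does not mention review by the participant.
- Section 5.3.1, the first intervention session, also takes place at Baseline visit 2: "The study team member will review the activPAL data and identify targetable prolonged SB bouts". Two goals are then set.
- Section 5.3.6 (Control Group) states: "Control group participants will receive all study assessment but will not be instructed to monitor sitting time". It does not say whether controls see their baseline report.
- Section 5.4 (Post-Intervention Visit) says that "all participants will be informed of their 24-hour glucose results and activity patterns retrieved from the activPAL device".

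Two further statements matter for size. Section 5.1, item 6 gives every participant a Fitbit: "All participants will have the ability to monitor physical activity, sleep, and heart rate with the Fitbit". Section 8.0 bases the sample size on an "effect size of 0.71 for reducing sitting time" from Sit Less V1, from which "we estimated a minimum sample size of 66".

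**The concern.** The protocol itself treats a reviewed activPAL report as a tool for changing behaviour. It opens the work of the goal-setting session in 5.3.1, and it is used again in the mid-program counselling session (5.3.5), where interventionist and participant go through the activity data together. The report also describes the outcomes of Aim 2, namely total sedentary time and the number of prolonged bouts.

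If controls see the same report with a staff member at the start of the 8 weeks, both arms share that element. Sharing it equally does not unbalance the arms, but any reduction in sitting that it causes among controls is subtracted from the between-arm difference. Section 8.0 plans to estimate effect sizes from this pilot, so what is at stake is mainly the size of that estimate. Power is secondary.

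**Working it through.** **1. Do controls get the review?** Setting the sections side by side:

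- Item 3 of 5.1 uses the same unqualified word for those who wear the device, which is everyone, and for those who review the report.
- Sections 5.2.1 and 5.2.2 list device return, download, storage and review by the PI. They list no review with participants.
- Section 5.3.1 has a study team member review the data at the same visit, for the intervention arm.

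The literal text of 5.1 therefore includes controls, and nothing excludes them. It remains possible that 5.1 and 5.3.1 describe one event. The order of participant review and allocation is not stated.

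**2. Direction.** Let D be the effect of the full package against a control without feedback, and F the effect of a single report review on controls. With the review shared, the trial estimates D − F. The proportion lost is f = F/D. If F is a reduction in sitting, the estimate moves toward zero. The documents give no value for F.

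**3. The plan's own figure.** Inputs from section 8.0 are d = 0.71 and a minimum of 66; 5.2.2 gives 1:1 allocation. Alpha, sidedness, power and dropout are not stated.

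- Normal approximation with two-sided 5% and 80% power (assumed): n per arm = 2 × (1.960 + 0.842)² / 0.71² = 31.1, rounded up to 32, or 64 in total.
- The t-test version gives 33 per arm, or 66 in total. This reproduces the stated minimum with no allowance for dropout.

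**4. Illustration under assumed dilution.** Diluted effect d′ = 0.71 × (1 − f). Power comes from the noncentral t distribution with noncentrality d′ × √(n/2) and 2n − 2 degrees of freedom. With f = 0 the noncentrality is 0.71 × √16.5 = 2.88 at 33 per arm (the minimum of 66) and 0.71 × √20 = 3.18 at 40 per arm (the target of 80, all analysed).

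| Assumed loss f | d′ | Total N for 80% power | Power, 33 per arm | Power, 40 per arm |
|---|---|---|---|---|
| 0% | 0.710 | 66 | 81.1% | 88.0% |
| 5% | 0.6745 | 72 | 77.0% | 84.6% |
| 10% | 0.639 | 80 | 72.5% | 80.6% |
| 20% | 0.568 | 100 | 62.3% | 70.8% |
| 30% | 0.497 | 130 | 51.1% | 59.3% |

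The f column is an assumption throughout. At the target of 80, power stays near 80% up to a loss of about 10%.

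**The case against.** The strongest reply is that exposure of controls is not established. The sentence in 5.1 sits in a device description under Baseline visit 1, the sections that set out Baseline visit 2 list no participant review, and the sentence may simply anticipate 5.3.1. Section 6.0 also uses the word participants without qualification for content that belongs only to the intervention, such as the water bottle. This stands as a reason for caution. It does not remove the need for a change, because staff who follow 5.1 as written would show controls the report.

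A second reply is that one past summary is not the intervention. Controls would get it without targeted bouts, goals, move alerts, bottle, texts or counselling, and seeing a summary is not an instruction to monitor sitting. This also stands: there is tension with 5.3.6 but no outright contradiction, and any dilution may be modest. Both arms share the Fitbit as well, with only the move alert switched off for controls, so removing the review would not make the control condition free of feedback.

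Third, a trial in which both arms see the report has a legitimate estimand: the effect of the package beyond assessment plus feedback. That is fair, but the plan does not say this is the intended contrast.

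Fourth, power is a poor measure of harm here. Section 8.0 plans exploratory mixed models and effect sizes and states no test. The control procedures of Sit Less V1 are not described either. If its controls saw their reports, 0.71 already contains the dilution. Both points stand, so the table is only an illustration.

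**Conclusion.** The concern holds in a limited form. Read literally, section 5.1 gives controls one element of the intervention, feedback on their own sitting, before the 8-week period. This may move the between-arm estimate of sedentary time toward zero.

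A reader might go further and infer that controls will certainly review their reports and that the contrast therefore shrinks. The documents do not support that. They leave the recipients and the order relative to allocation unclear, and they give no effect for a single review. A reader might also take the 10% to 30% rows as a forecast. They rest on assumed dilution, an assumed two-sided 5% t-test, no dropout, and a 0.71 free of the same dilution in V1. Nor does the point extend to glucose data: section 5.2.1 lists only the download of CGM results at Baseline visit 2, with no review with participants.

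The change is still worth making, because it is specific, costs little and settles the ambiguity under either reading.

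**What to change.** - Amend 5.1 item 3 and 5.2.2 so that at Baseline visit 2 the activPAL data are downloaded and the participant is randomised before any report is shown to a participant.
- State that the report is then reviewed only with intervention participants, as the first step of 5.3.1.
- State in 5.3.6 and 5.4 that controls receive their baseline activPAL summary after the post-intervention 7-day wear, together with the activity feedback that 5.4 already promises to all. The wording should say after the wear rather than at the visit, because the wear starts at that visit and the devices come back by mail. It should also say that baseline data are included, which 5.4 leaves open.

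No change to the handling of CGM results is proposed.

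The cost is protocol wording, with no added visits, measurements or sample size. Controls wait about 9 weeks (8 weeks of intervention plus the 7-day wear) for feedback they will still receive.

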### 4. Continuous Glucose Monitor (CGM)

The device (FreeStyle Libre Pro™; Abbott Diabetes Care, Witney, Oxon, UK) will be worn on the back of the upper arm to measure their 24-hours glucose levels for 7 days. The CGM has one sensor applicator, one sensor, and one reader. Skin will be prepared using an alcohol wipe and the sensor applicator will be placed over the application site. The research staff will press firmly, hold for a few seconds, and gently pull the sensor applicator away from the site. A sensor applicator has an introducer needle which will be retracted after application. Only a thin, flexible filament will remain under the skin and the sensor is held in place by an adhesive. The sensor applicator serves as a container for disposal. The water-proof sensor, worn on the upper arm, is factory calibrated. The reader is retained by the PI and data are not visible to participants during sensor wear. The sensor automatically captures and stores glucose data every 15 min (96 glucose readings/day).

### 5. Sleep diary and wear log

The participants will be asked to complete a daily sleep diary each morning while they are wearing the monitor, which takes about 2 minutes. The participant will also complete a daily wear log each evening. The information about sleep onset and offset and wear time will be used to validate the activPAL wearing protocol.

Once they complete the 7 days of activPAL and CGM monitoring, they will be scheduled for the in-person visit (Baseline visit 2) and will return the devices and log to the study team at the visit.

#### 6. Fitbit

We will provide Fitbit (Inspire 3) to each participant. The Fitbit is not intended to be used as a medical device. All participants will have the ability to monitor physical activity, sleep, and heart rate with the Fitbit. All data from the Fitbit will be continuously streamed to the secure Fitbit servers. The study team member will assist participants in downloading the app and creating an account and will instruct them on how to use the device, with the official Fitbit user manual. When we create Fitbit accounts for research subjects, we do not use their real name or email address and default their account settings to the most privacy-protective option available.

Fitbit accounts require a unique email address for each user. To ensure participants' anonymity and privacy when creating Fitbit accounts, we will (1) set up anonymous Gmail accounts and (2) set up de-identified Fitbit accounts for the purpose of the study. This individualized email address will then be linked to a Fitbit account in which personal identifiers should not be used. Importantly, research staff and participants will be advised that the email and Fitbit accounts should be used strictly for the study's purpose.

Moreover, account information will be stored in protected PI's computer within encrypted documents. Once the intervention is concluded, Fitbit data will not be collected. Also, Fitbit and Fitbit app will be reset for the participant to keep using the Fitbit after study completion.

#### 5.2 Baseline visit 2

#### 5.2.1 Baseline assessment

The in-person baseline visit 2 will take place at the VUSN Clinic in the Wesley building. Participants will return the activPAL and the continuous glucose monitoring devices at Baseline visit 2. Participants will receive \$25 for baseline visit 2.

### 1. ActivPAL data download

The 7 days of activPAL data will be downloaded and stored in the secured PI's computer. The variables of interest from the activPAL data are listed below:

- A) Sedentary behavior: SB will be objectively measured as time spent sedentary (sitting or lying, minutes/day) and number of prolonged sedentary bouts (>30 minutes and >60 minutes) using the activPAL3. ActivPAL data will be downloaded and processed using activPAL software.
- B) **Physical activity**: Time spent standing and walking (stepping), number of sitting- to-standing transitions, and daily step counts will be measured using the activPAL.

### 2. Continuous glucose monitoring data download

The 7 days of CGM data will be downloaded via Libreview and stored in the Pl's computer. The variables of interest from the CGM data are listed below: The 24-hour glucose control: the 24-hour glucose control will be evaluated by mean 24-hour glucose levels and numbers of events and time in hypoglycaemia (glucose < 3.9 mmol/l), euglycaemia (glucose 3.9–7.8 mmol/l), hyperglycaemia (glucose > 7.8 mmol/l) and above target (glucose > 9 mmol/l).

### 5.2.2 Randomization

Once the data is downloaded and reviewed by the PI, the Study Team Member will use the REDCap randomization function and will inform participants of their group assignment (1:1 ratio).

